5.4.2 Permitted Concomitant Therapy Requiring Caution and/or Action

Based on the in vitro studies, both EGF816 and gefitinib are metabolized by CYP3A4. Moderate inhibitors and inducers of CYP3A4 should be used with caution and strong inhibitors and strong inducers of CYP3A4 should not be used concomitantly with either drug. Grapefruit juice is a CYP3A4 inhibitor, therefore, consumption of grapefruit or grapefruit juice should be avoided during study treatment.

EGF816 is a P-gp substrate. Co-administration of EGF816 with P-gp inhibitors may increase systemic exposure and/or alter tissue uptake of EGF816. EGF816 is a moderate inhibitor of BCRP with IC50 value of 4  $\mu$ M. The exposure of BCRP substrate may increase when coadministered with EGF816. EGF816 is an inhibitor of the human multidrug and toxin extrusion transporter 1 and 2-K (MATE1 and MATE2-K) with an IC50 of 0.70 and 4.6  $\mu$ M respectively. As a result EGF816 has potential to increase the exposure of co-medications whose clearance is significantly

mediated by MATE. In the absence of data confirming whether such an interaction occurs in patients, caution should be exercised when potent P-gp inhibitors and MATE or BCRP substrates are concurrently used. The patient and the Investigator should be aware of potential signs of overdose of the concomitant medication. In the event of suspected toxicity, administration of either EGF816 or concomitant drugs should be discontinued according to Investigator judgment. Refer to Appendix B, Table 13-1, for permitted medications that require caution and Appendix B, Table 13-2 for a list of prohibited medications.

Live vaccines (e.g., intranasal influenza, measles, mumps, rubella, oral polio, BCG, yellow fever, varicella, and TY21a typhoid vaccines) should not be administered while a patient is dosed with EGF816 and for 30 days after the last dose of EGF86. Refer to Appendix B, Table 13-1, for permitted medications that require caution and Appendix B, Table 13-2 for a list of prohibited medications. If a patient must use a drug in Appendix B, Table 13-2, the patient must be discontinued from the study.

Drugs that elevate gastric pH (e.g., proton pump inhibitors, histamine H2-receptor antagonists, and antacids) may reduce plasma concentrations of gefitinib. Avoid concomitant use of gefitinib with proton pump inhibitors, if possible. If treatment with a proton-pump inhibitor is required, take gefitinib 12 hours after the last dose or 12 hours before the next dose of the proton-pump inhibitor. Take gefitinib 6 hours after or 6 hours before an H2-receptor antagonist or antacid.

# 5.5 Criteria for Taking a Participant Off Protocol Therapy

The duration of treatment will depend on response and tolerance. In the absence of treatment delays due to adverse events, EGF816 and gefitinib may be continued until there is disease progression by RECIST 1.1. Patients may continue treatment beyond disease progression determined by RECIST if they are deemed to be deriving ongoing clinical benefit from treatment by the treating investigator.

Participants will also be removed from the study if any of the following criteria apply:

- Clinically significant disease progression
- Intercurrent illness that prevents further administration of treatment
- Unacceptable adverse event(s)
- Participant demonstrates an inability or unwillingness to comply with the oral medication regimen and/or documentation requirements
- Participant decides to withdraw from the protocol therapy
- General or specific changes in the participant's condition render the participant unacceptable for further treatment in the judgment of the treating investigator
- Lost to follow-up
- Withdrawal of consent for data submission
- Death

Participants will be removed from the protocol therapy when any of these criteria apply. The reason for removal from protocol therapy, and the date the participant was removed, must be documented in the case report form (CRF). Alternative care options will be discussed with the participant.

An ODQ Treatment Ended/Off Study Form will be filled out when a participant is removed from protocol therapy. This form can be found on the DF/HCC website at http://www.dfhcc.harvard.edu/research/clinical-research-support/document-library-forms-sopsetc/.

In the event of unusual or life-threatening complications, treating investigators must immediately notify the Overall PI, [name] at [contact].

## 5.6 Duration of Follow Up

Participants will be followed for 30 days (+/- 7) after removal from study for adverse event assessment, or until all AEs present at end of treatment have resolved or stabilized. Patients will then be monitored every 3 months until death for survival follow up.

## 6. DOSING DELAYS/DOSE MODIFICATIONS

Dose delays and modifications will be made as indicated in the following table(s). The descriptions and grading scales found in the revised NCI Common Terminology Criteria for Adverse Events (CTCAE) version 4.0 will be utilized for dose delays and dose modifications. A copy of the CTCAE version 4.0 can be downloaded from the CTEP website http://ctep.cancer.gov/protocolDevelopment/electronic\_applications/ctc.htm.

Dose delays and modifications will be made as indicated in the following table(s). The descriptions and grading scales found in the revised NCI Common Terminology Criteria for Adverse Events (CTCAE) version 4.0 will be utilized for dose delays and dose modifications. A copy of the CTCAE version 4.0 can be downloaded from the CTEP website http://ctep.cancer.gov/protocolDevelopment/electronic applications/ctc.htm.

EGF816 and gefitinib are both EGFR tyrosine kinase inhibitors and have both overlapping and distinct toxicities. Guidelines for the management of potentially drug-related toxicities, including dose interruptions and dose reductions of each drug, are provided in section 6.1.

When possible, toxicities should be managed with appropriate medical treatment (including antiemetics, anti-diarrheals, etc.) Other contributing factors, including concomitant medications which may be contributing to the toxicity, should be identified and discontinued or dose reduced if appropriate. The following sections provide guidelines for dose modification and dose interruption (i.e., interruption and re-initiation criteria for EGF816 and gefitinib treatment). All dose modifications should be based on the worst preceding toxicity (CTCAE version 4.0). If, due to study drug related toxicity, a patient requires a dose interruption of >28 days from the intended day of the next scheduled dose, then the patient must be discontinued from the study treatment. Each patient is allowed no more than two dose reductions of each study drug. In addition, a patient must discontinue treatment with EGF816 and gefitinib if, after treatment is resumed at a lower dose, the toxicity recurs with the same or worse severity.

Exceptions can be made on a case by case basis after discussion with the Principal Investigator. In exceptional cases, after discussion with the PI, patients may be allowed to continue treatment or resume treatment with only one of the investigational drugs. All interruptions or modifications must be recorded on the Dosage Administration Record CRF.

In case of study treatment interruption, visit schedule should still be followed and assessments performed as per Table 10-1 (study calendar.)

## 6.1 Conditions requiring dose modification:

The dose modification levels for EGF816 are as follows:

Dose Level	EGF816 Dose
0	100 mg once daily
-1	75 mg once daily
-2	50 mg once daily

#### Table 6-1: EGF816 dose reduction

The dose modification levels for gefitinib are as follows:

L	able 6-2: Gentinib dose reduction		
Dose Level		Gefitinib Dose	
	0	250 mg once daily	
	-1	250 mg every other day	

# Table 6-2: Gefitinib dose reduction

General guidelines for dose of modifications of EGF816 and gefitinib for all toxicities that are at least possibly related to study drug are listed in table 6-3. Please see sections 6.1.1-6.1.6 for detailed guidelines for management of specific toxicities including pneumonitis/interstitial lung disease, liver function abnormalities, diarrhea, rash and cardiac toxicities. Modifications to these recommended guidelines may be made individual cases based on the clinical judgment of the treating investigator.

Recommended Dose Modifications	
Worst toxicity	Action
CTCAE Grade	
Grade 1	Maintain dose level of both drugs
Grade 2	Maintain dose level of both drugs
Grade 3	Omit both EGF816 and gefitinib until resolved to
	$\leq$ Grade 1. When the toxicity has resolved to grade

	1 or less, reintroduce drugs one at a time with one
	dose-level reduction in each drug. EGF816 should
	be reintroduced first a and the patient should then
	be monitored closely for recurrence of the AE for
	at least 7 days; if there is no recurrence of > grade
	1 AE, gefitinib can then be reintroduced.
Grade 4	Permanently discontinue treatment.

**A.** The order of drug reintroduction can be changed in clinical circumstances where the treating investigator feels it would be indicated to reintroduce gefitinib first.

6.1.1 Management of Pneumonitis/Interstitial Lung Disease

CTCAE Grade	Required investigations	Management of pneumonitis	Action and dose modification
Grade 1 Asymptomatic, radiographic findings only	CT Chest; repeat at least every 2 cycles until radiographic abnormalities resolve.	No specific therapy required.	Continue both drugs with close monitoring for the development of symptoms.
Grade 2 Symptomatic, not interfering with activities of daily living (ADLs)	CT Chest Consider PFTs a Repeat scan at least every other cycle until radiographic abnormalities resolve. Consider bronchoscopy with biopsy and /or bronchoalveolar lavage (BAL) c .	Symptomatic only. Consider corticosteroids b if symptoms are clinically significant.	Interrupt both drugs until improvement to $\leq$ Grade 1. If symptoms resolve to $\leq$ Grade 1 in $\leq$ 7 days, reduce both gefitinib and EGF816 by 1 dose level and reintroduce one at a time as above. If symptoms fail to resolve within 7 days or recur after resumption of study drug at decreased dose, permanently discontinue both study drugs.
Grade 3 Symptomatic, interfering with ADL; O2 indicated	CT Chest and Pulmonary Function Testing (PFTs) Repeat scan at least every cycle until radiographic	Short course of corticosteroids b to be considered if infective origin is ruled out.	Permanently discontinue both study drugs.

٦

	abnormalities resolve. Bronchoscopy with biopsy and/or BAL c is recommended.		
Grade 4 Life threatening; ventilator support indicated	CT Chest and required PFTs, if possible (including spirometry, DLCO, and room air O2 saturation at rest.) Repeat scan at least every cycle until return to within normal limits. Bronchoscopy with biopsy and / or BAL c is recommended, if possible.	Short course of corticosteroids b to be considered if infective origin is ruled out.	Permanently discontinue both study drugs.
A PFT (Pulmonary function tests) to include: diffusing capacity corrected for hemoglobin (DLCO); spirometry; resting oxygen saturation. Guideline for significant deterioration in lung function: Decrease in spirometry and/or DLCO of $20\%$ and/or O2 saturation $\leq 88\%$ at ract on room air			

30% and/or O2 saturation  $\le 88\%$  at rest on room air. B Duration and dose of course of corticosteroids will vary according to circumstances but should be as limited as possible. C If bronchoscopy is performed, bronchoalveolar lavage (BAL) should be done where possible to exclude alveolar

hemorrhage, opportunistic infections, cell count + determination lymphocyte CD4/8 count where possible.

# 6.1.2 Management of liver function abnormalities (bilirubin, AST, ALT)

# Table 6-4: Guidelines for management of abnormal LFTs: Investigations (Henatic)a

Investigations (Hepatic) a		
Total Bilirubin (for patients with Gilbert Syndrome these dose modifications apply to changes in		
direct [conjugated] bilirubin only)		
Grade 1 (>ULN and $\leq 1.5 \times ULN$ )	Maintain dose level with liver function test	
	(LFTs) monitored as per protocol	
Grade 2 (>1.5 and $\leq$ 3.0 x ULN) with ALT or	Omit both drugs until resolved to $\leq$ grade 1, then:	
$AST \leq 3.0 x ULN$	If resolved in $\leq$ 7 days, then resume EGF816 at	
	the original dose level with close LFT	
	monitoring. Resume gefitinib at the original dose	
	level if LFTs remain < g rade 1 after 7 days of	
	EGF816.	
	If resolved in $>7$ days, then resume drugs one at a	

	time (as above) with one level dose reduction in each drug.
Grade 3 (>3.0 and ≤10.0 x ULN) with ALT or AST ≤3.0 x ULN	Omit both drugs until resolved to $\leq$ grade 1, then: If resolved in $\leq$ 7 days, resume EGF816 with one level dose reduction and close LFT monitoring. Resume gefitinib with one level dose reduction if LFTs remain $\leq$ grade 1 after 7 days of EGF816. If resolved in $\Box$ 7 days discontinue patient from study treatment.
	The patient should be monitored weekly (including LFTs b ), or more frequently if clinically indicated, until total bilirubin has resolved to baseline or stabilized over 4 weeks.
Grade 4 (>10.0 x ULN)	Permanently discontinue study treatment. The patient should be monitored weekly (including LFTs), or more frequently if clinically indicated, until total bilirubin has resolved to baseline or stabilized over 4 weeks.
AST or ALT	
Grade 1 (>ULN and $\leq 3.0 \text{ x ULN}$ )	Maintain dose level with LFTs monitored per protocol
Grade 2 (>3.0 and ≤5.0 x ULN) without total bilirubin elevation to >2.0 x ULN	Maintain dose level with LFTs monitored per protocol
Grade 3 (>5.0 and ≤20.0 x ULN) without total bilirubin elevation to >2.0 x ULN	Omit both drugs until resolved to $\leq$ Grade 1 (or to baseline), then resume EGF816 with one level dose reduction and close LFT monitoring. Resume gefitinib with one level dose reduction if LFTs remain $\leq$ grade 1 after 7 days of EGF816. Permanently discontinue study treatment if $\geq$ Grade 3 elevation recurs.
	If AST or ALT > 5 x ULN in patients with baseline AST or ALT $\leq$ 3 x ULN, or if AST or ALT > 8 x ULN in patients with baseline AST or ALT > 3 x ULN but $\leq$ 5 x ULN, immediate testing for viral hepatitis infection or reactivation should be performed , see Section 6.1.3. Patients who have HBV-DNA monitoring during the study should be an tested immediately
Grade 4 (>20.0 x ULN) without total bilirubin elevation to >2.0 x ULN	during the study should be re-tested immediately.Omit both drugs until resolved to ≤ Grade 1 (or to baseline), then resume EGF816 with one level dose reduction and close LFT monitoring.Resume gefitinib with one level dose reduction if

LFTs remain $\leq$ grade 1 after 7 days of EGF816.
However, permanently discontinue study
treatment if the elevation of Grade 4 recurs.
If AST or ALT>20.0 x ULN immediate testing
for viral hepatitis infection or reactivation
should be performed, see Section 6.1.3. Patients
who have HBV-DNA monitoring during the
study should be retested immediately.

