As of the data cutoff date of 18-Dec-2015, 142 patients (95.9%) who were treated with EGF816 capsules or tablets experienced at least one AE of any grade, regardless of relationship to the study drug. The most frequent AEs (all CTCAE grades, >10% of patients) regardless of study drug relationship at the seven dose levels specified below were rash (group term) (56.1%), diarrhea (41.9%), maculopapular rash , pruritus (36.5%), fatigue (27.0%), stomatitis (27.0%), dry skin (24.3%), nausea (23.6%), cough (20.9%), decreased appetite (20.3%), vomiting (14.9%), constipation (14.2%), headache (12.8%), anemia (12.2%), paronychia (11.5%), pyrexia (11.5%), dyspnea (10.8%), edema peripheral (10.8%), back pain (10.1%), and upper respiratory tract infection (10.1%)

One-hundred thirty-four (90.5%) patients experienced AEs of any grade that were suspected to be related to EGF816. The most frequent (>10% of patients) AEs of any CTCAE grade suspected to be related to EGF816 were rash (group term) (52%), diarrhea (36.5%), pruritus (33.8%), dry skin (24.3%), stomatitis (24.3%), fatigue (16.2%), nausea (15.5%), decreased appetite (12.2%), and vomiting (10.1%)

Seventy (47.3%) patients who were treated with EGF816 capsules or tablets at the dose levels specified below experienced Grade 3 or Grade 4 AEs regardless of relationship to the study drug. Grade 3/4 AEs occurring in  $\geq 2\%$  of patients were rash (grouped term) (15.5%), anemia (5.4%), pneumonia (5.4%), diarrhea (4.7%), fatigue (2.7%), dyspnea (2.7%), urticaria (2.7%), hypertension (2.7%), stomatitis (2.0%), decreased appetite (2.0%), hyperuricemia (2.0%), and seizure (2.0%).

Forty-four patients (29.7%) experienced Grade 3/4 AEs that were suspected to be related to EGF816. Those occurring in  $\geq 1\%$  of patients were rash (group term) (15.5%), anemia (2.7%), urticaria (2.7%), diarrhea (2.0%), fatigue (2.0%), stomatitis (2.0%), HBV (1.4%), and increased lipase (1.4%).

As of the data cutoff date (18-Dec-2015), SAEs, regardless of study drug relationship, were

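### Table 6-4 does not settle whether a Grade 3 AST/ALT recurrence after a first Grade 4 rise forces a permanent stop; read by the first-event row, the rule is looser after the worse liver injury.

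*Combined protocol and SAP*

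**What the plan says.** Table 6-4 has two rows for high AST or ALT without a marked bilirubin rise.

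- **Grade 3 row** ("Grade 3 (>5.0 and ≤20.0 x ULN) without total bilirubin elevation to >2.0 x ULN"): hold both drugs until recovery, restart EGF816 one level lower, then gefitinib one level lower if liver tests stay at Grade 1 or below after 7 days. The permanent-stop trigger is "Grade 3 elevation recurs", with a greater-than-or-equal sign before it in the cell.
- **Grade 4 row** ("Grade 4 (>20.0 x ULN) without total bilirubin elevation to >2.0 x ULN"): the same hold and the same stepwise restart. The permanent-stop trigger is "treatment if the elevation of Grade 4 recurs". A Grade 3 recurrence is not mentioned.

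Section 6 adds two general rules. The first is "All dose modifications should be based on the worst preceding toxicity". The second requires discontinuation if, "after treatment is resumed at a lower dose, the toxicity recurs with the same or worse severity".

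Table 6-2 lists one reduced gefitinib level, "250 mg every other day". Table 6-1 lists two for EGF816, 75 mg and 50 mg.

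**The concern.** The two rows prescribe the same management except for the trigger that ends treatment, and that trigger is stricter in the row for the milder injury. A site following the row of the first event would have to stop a patient whose first ALT was 6 x ULN and who returns at 10 x ULN. It would not have to stop a patient whose first ALT was 25 x ULN and who returns at the same 10 x ULN. A site following the row of the current value would stop both.

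The stake is patient safety: possible further re-exposure after a rise above 20 x ULN and a second rise above 5 x ULN, with the decision depending on how a site reads the table.

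**Working it through.** No sample-size or power figure is involved. The check has three parts.

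**1. Forced stop by first and recurrent grade (isolated rises, after restart at a lower dose)**

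| First rise | Recurrence | Row of first event | Row of new event | Section 6 general rule |
|---|---|---|---|---|
| Grade 3 | Grade 3 | stop | stop | stop (same) |
| Grade 3 | Grade 4 | stop | no stop: first Grade 4 | stop (worse) |
| Grade 4 | Grade 4 | stop | stop | stop (same) |
| Grade 4 | Grade 3 | **no forced stop** | **stop** | no forced stop (milder) |

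Only the last line is left open. In the second line Section 6 forces the stop whichever row is used. In the last line Section 6 forces nothing, so the answer depends on which row governs.

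By the first-event row, the stop threshold is >5 x ULN after Grade 3 and >20 x ULN after Grade 4, a ratio of 20/5 = 4. Recurrences from >5 to 20 x ULN after a Grade 4 rise carry no mandatory stop.

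**2. Does other text decide it?**

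- The worst-preceding-toxicity rule in Section 6 points to the Grade 4 row.
- The greater-than-or-equal sign in the Grade 3 row covers a Grade 4 recurrence, which a row meant only for current values of >5 to 20 x ULN would not need to do. This also suggests first-event wording.
- On the other side, a value of 10 x ULN falls numerically in the Grade 3 row, and a first Grade 4 rise was itself Grade 3 or higher, so such a rise has recurred.
- Footnote c of Table 6-4 asks for conservative action, but for combined AST/ALT and bilirubin rises below the combined thresholds, not for isolated rises.
- Table 6-3 stops permanently at a first Grade 4 toxicity. Table 6-4 relaxes that for AST/ALT, so here the recurrence trigger is what limits rechallenge.

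The permissive reading also meets a dose gap. After the first Grade 4 rise, EGF816 goes from 100 to 75 mg and gefitinib to its lowest listed level. If a Grade 3 recurrence on both drugs called for another one-level cut, EGF816 could go to 50 mg, but gefitinib has no level left.

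**3. How many patients?**

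Section 2.2.2 gives 148 patients on single-agent EGF816. It lists Grade 3/4 events of any cause in at least 2% of patients, and those suspected to be related in at least 1% (the latter list ends with "HBV (1.4%), and increased lipase (1.4"%). Neither ALT nor AST elevation is on either list.

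- Any cause: 3/148 = 2.03% would be listed, so at most 2/148 = 1.35% for each term. Expected in 36: 36 x 2/148 = 0.49.
- Suspected related: 2/148 = 1.35% would be listed, so at most 1/148 = 0.68%. Expected in 36: 36 x 1/148 = 0.24.
- Exact (Clopper-Pearson) upper 95% limit for 2/148: the 0.975 quantile of Beta(3, 146) = 4.8%. In 36: 36 x 0.04796 = 1.73.
- The documents give no rate for the combination. Assuming 0 to 10%: 36 x 0 = 0 to 36 x 0.10 = 3.6 patients.

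These counts are for any Grade 3/4 rise. The open case needs an isolated Grade 4 rise, recovery, restart and then recurrence at >5 to 20 x ULN, which is a subset.

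**The case against.** The best counter-argument is that clinicians use such a table by looking up the value in hand. An ALT of 10 x ULN sits only in the Grade 3 row, whose last sentence then stops the patient. On this view the first-event reading is strained: applying the Grade 4 row to every later value would mean holding both drugs for a trivial rise. Section 6's worst-preceding rule concerns dose modification and does not cancel another row's stop rule. Its same-or-worse test requires a stop in some cases without saying that treatment stops only then.

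Much of this stands. The current-value reading is fair and gives the safer answer. But the protocol does not say that it governs, and the Section 6 wording leans the other way. The first-event reading does not require the Grade 4 row to govern every later value, only that each row's recurrence clause refers back to the event in that row.

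Two further points are partly right. The difference may be deliberate, since it matches Section 6's general test; if so, the table should say so. The missing second gefitinib level is a wider matter, because Section 6 allows up to two reductions of each drug; the edit proposed here removes it only for this case.

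The safeguards are real. Both drugs are held at a Grade 3 recurrence under either row, viral hepatitis testing and the combined ALT/bilirubin stop rule apply, interruption is capped at 28 days, and investigator judgment and exceptions agreed with the Principal Investigator remain. They limit harm but set no default for the open case.

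**Conclusion.** The concern holds as an ambiguity: the text supports two readings of a Grade 3 recurrence after a Grade 4 rise, and one of them is less strict after the worse injury. Whether that was intended cannot be told from the documents.

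The size is small, probably 0 or 1 of 36 patients. That judgement rests on single-agent data and on the listing thresholds in Section 2.2.2; the 0 to 10% range for the combination is an assumption, and no document gives a rate for the full sequence of events. The primary endpoint, sample size and analysis do not depend on this rule. It merits correction because the consequence for an affected patient could be serious and the correction is cheap.

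**What to change.** In the AST/ALT Grade 4 row of Table 6-4, make the permanent-stop trigger a recurrence of Grade 3 or higher, as in the Grade 3 row. Both readings then give the same answer, and the gefitinib dose gap no longer arises in this situation. The protocol already uses this kind of trigger for rash: Table 6-10 ends EGF816, and Table 6-11 all study treatment, after more than one episode of Grade 3 or higher.

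If the present difference is intended, state in the Grade 4 row what to do on a Grade 3 recurrence, including the gefitinib dose.

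The cost is one table cell at the next amendment, with no added tests, visits or patients. The downside is that a rare patient may stop treatment earlier than under the looser reading.
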